VRE	Vancomycin Resistant Enterococcus

< This page is intentionally left blank >

PROTOCOL SUMMARY

Title:	A Randomized Controlled Trial of Encapsulated Fecal Microbiota for Vancomycin Resistant Enterococcus Decolonization
Phase:	II
Population:	Vancomycin resistant enterococcus (VRE) identified by stool culture in the past 14 days among adults.
Sample size	46 (1:1 randomization) - 23 in the treatment group and 23 in the placebo group).
Number of sites:	Multi-center study at 2 tertiary academic medical centers (Indiana University and University of Wisconsin).
Study duration:	Approximately 1 year.
Description of Agent:	Encapsulated fecal microbiota preparation (formulation FMP-402). Please refer to OpenBiome BBMF # 17300, Section I, H. Sourced from human-derived microbes. Please refer to OpenBiome BBMF # 15543, Section F.

Study Objectives: To investigate the efficacy and safety of FMP-402 to decolonize VRE.

Primary Objectives:

- To determine the VRE decolonization rate of FMP-402 versus placebo.
- To evaluate the safety profile for FMP-402 versus placebo.

Secondary Objectives:

- To determine the VRE infection rate of FMP-402 versus placebo.
- To evaluate the decolonization rate of antibiotic resistant bacteria (ARB) for FMP-402 versus placebo.
- To determine the composite ARB infection rate for FMP-402 versus placebo.
- To evaluate the time to VRE colonization and infection.
- To evaluate the VRE decolonization rate for FMP-402 versus placebo among immunocompromised patients.
- To evaluate VRE decolonization rate for FMP-402 versus placebo among those 65 years and older.

Exploratory Objectives:

- To evaluate the microbiome disruption index (MDI) by 16s rRNA sequencing): MDI-community and MDI-species (day 3, day 10, week 4).
- To evaluate the trends in VRE type/strain-level engraftment using whole genome sequencing among those colonized.

**Study
Endpoints/Outcome
Measures:**

Primary Efficacy Outcome Measure:

- Proportion of participants with VRE decolonization at day 10 (± 3 days) after randomization.
 - VRE decolonization is defined by absence of VRE on stool culture using standard clinical laboratory techniques.

Secondary Efficacy Outcome Measures:

- Proportion of participants with VRE infection at day 3 (± 2), day 10 (± 3), week 4 (± 5 days) after randomization.
 - VRE infection will be defined as an associated bacteremia, urinary tract infection, or wound-related infection.

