Secondary Objectives:

- To determine the VRE infection rate of FMP-402 versus placebo.
- To evaluate the decolonization rate of antibiotic resistant bacteria (ARB) for FMP-402 versus placebo.
- To determine the composite ARB infection rate for FMP-402 versus placebo.
- To evaluate the time to VRE colonization and infection.
- To evaluate the VRE decolonization rate for FMP-402 versus placebo among immunocompromised patients.
- To evaluate VRE decolonization rate for FMP-402 versus placebo among those 65 years and older.

Exploratory Objectives:

- To evaluate the microbiome disruption index (MDI) by 16s rRNA sequencing): MDI-community and MDI-species (day 3, day 10, week 4).
- To evaluate the trends in VRE type/strain-level engraftment using whole genome sequencing among those colonized.

C.3.2 Study Outcome Measures**C. 3.2.1 Efficacy Outcome Measures****Primary Efficacy Outcome Measure:**

- Proportion of participants with VRE decolonization at day 10 (± 3 days) after randomization.
 - VRE decolonization is defined by absence of VRE on stool culture using standard clinical laboratory techniques.

Secondary Efficacy Outcome Measures:

- Proportion of participants with VRE infection at day 3 (± 2), day 10 (± 3), week 4 (± 5 days) after randomization.
 - VRE infection will be defined as an associated bacteremia, urinary tract infection, or wound-related infection.
- Proportion of participants with other antibiotic resistant bacteria (ARB) colonization at day 10 (± 3) after randomization. ARB testing will be conducted with Acuitas™ MDRO test (OpGen) or similar PCR assay platform.
 - ARB will be defined as: a) carbapenem-resistant enterobacteriaceae (CRE) by PCR; b) extended-spectrum beta-lactamase (ESBL) producing organism by PCR; c) *C. difficile* by PCR.
- Proportion of participants with antibiotic resistant bacteria (ARB) colonization at day 10 (± 3) after randomization. ARB testing will be conducted with AcuitasTM MDRO test (OpGen) or similar PCR assay platform.
 - ARB will be defined as: a) carbapenem-resistant enterobacteriaceae (CRE) by PCR; b) extended-spectrum beta-lactamase (ESBL) producing organism by PCR; c) *C. difficile* by PCR; d) VRE

- Proportion of participants with composite ARB infection at day 3 (± 2), day 10 (± 3), week 4 (± 5 days) after randomization and time (in days) when ARB infection occurs.

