 - Adverse events (NIH criteria)
- Stool collection for 16S sequencing and ARB PCR

Participants will be asked if study staff may follow participants passively using their medical records if clinical follow-up and/or stool collection is not viable.

All attempts will be made to complete safety follow-up for participants who received the study product, but discontinued participation in other study procedures, for the duration of the planned follow-up period.

C.7.5 Unscheduled Visit

At the time of VRE infection (for participants who experience an infection) or serious AE. Study staff will attempt to collect a stool sample (optional).

Additionally, VRE isolates from the site of associated VRE infection (blood, urine, wound) will attempt to be collected (optional) for participants suspected to have a VRE infection.

- Study staff will complete an infection CRF for each ARB infection episode. This CRF will be used to track duration of the episode, type, dosage and duration of antibiotics.
- Data points for infectious episode
 - Date
 - Preliminary diagnosis
 - Antibiotic/s
 - Name
 - Formulation (IV, suspension, capsules)
 - Dosage
 - Prescribed duration
 - Final (actual) duration of antibiotics
 - Change in antibiotics regime
 - Concomitant medication (Name, dose, route of administration, duration)
 - Hospital admission (yes/no)
 - Name of facility
 - Department where participant was admitted (ward / step down/ ICU)
 - Relevant medical procedures
 - Colonoscopy (including preparation)
 - Intestinal surgery
 - Dialysis
 - Other
 - Final diagnosis

- For a serious AE (section 8.5), the details of reporting are outlined in Section 8.7

C.7.6 Stool Collection

Stool samples will be collected (or rectal swabs in keeping with VRE standard of care). If the visit is conducted over the telephone, participants will be given instructions on how to mail in or drop off their stool sample, depending on their preference:

- a) Screening (only if status of VRE colonization is not already known)
- b) Enrollment – if needed (VRE positive screened sample 14 days prior to Enrollment visit is acceptable).
- c) Day 3 (± 2) after randomization
- d) Day 10 (± 3) after randomization
- e) Week 4 (± 5) after randomization

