Monitoring visits will include, but are not limited to, review of regulatory files, accountability records, eCRFs, informed consent forms, medical and laboratory reports, and protocol compliance. Study monitors will meet with site PIs to discuss any problems and actions to be taken and document visit findings and discussions.

C.10. STATISTICAL CONSIDERATIONS

This is a randomized double blind, placebo controlled clinical trial to determine the safety and efficacy of FMP-402 on the decolonization of VRE.

C.10.1 Sample Size

Sample size (n=46) was calculated based on a conservative estimate of 85% decolonization in FMT group, 40% in control group with power=0.9 and alpha=0.05 in keeping with preliminary data and a conservative 15% drop-out rate.

C.10.2 Final Analysis Plan

Categorical data will be described using descriptive statistics (proportions and percentages). Continuous data will be described using means and standard deviations (normally distributed data) or using medians and interquartile range (non-parametric data). Appropriate comparative statistical tests will be chosen based in the variable types (categorical, dichotomous, continuous) and distribution (parametric, non-parametric) and will be used to describe significant differences between intervention and control groups. Where appropriate, point estimates and confidence intervals will be reported. The p-value will be two tailed with a significance level of 0.05.

C.11. SOURCE DOCUMENTS AND ACCESS TO SOURCE DATA/DOCUMENTS

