Affiliations: (1)OpenBiome, Medford, MA, (2)Harvard Medical School, Boston, MA, (3)Brigham and Women's Hospital, Boston, MA, (4)Montefiore Medical Center, Bronx, NY, (5)OpGen, Gaithersburg, MD, (6)Indiana University, Indianapolis, IN, (7)Icahn School of Medicine at Mount Sinai, New York, NY, (8)The Warren Alpert Medical School of Brown University, Providence, RI, (9)University of Alabama at Birmingham, Birmingham, AL

Background: Vancomycin-resistant enterococcus (VRE) is a public health threat to hospitalized patients and gastrointestinal colonization with VRE is a major risk factor for active infection, including bacteremia. Fecal microbiota transplantation (FMT) is a well-tolerated and effective treatment for recurrent *C. difficile* (rCDI). Data from animal models and clinical case reports suggest that FMT may reverse dysbiosis and eliminate colonization with antibiotic-resistant organisms, including VRE; however, there is a paucity of clinical data. This study aims to determine whether FMT may decolonize VRE in rCDI patients treated with FMT.

Methods: A multicenter retrospective analysis was performed using stool samples from rCDI patients treated with FMT (n=31) or autologous FMT as a control (n=18). Material was accessed from 6 academic hospitals under existing research protocols. VRE was assessed using a PCR-based assay targeting VanA (Acuitas® MDRO Gene Test). Colonization was defined as positive result at any dilution. VRE decolonization was defined as absence of VRE colonization post-FMT among a patient colonized with VRE pre-FMT.

Results: Among the cohort, 9/31 (29%) of patients in the FMT group and 7/18 (39%) of patients in the control group were colonized with VRE at baseline. At the first time point measured post-FMT, 9/9 (100%) of colonized patients in the FMT group tested VRE-negative compared to 3/7 (43%) in the control group

($p=0.02$, Fisher's Exact Test). On subgroup analysis, samples collected at ≤ 6 weeks, 5/5 (100%) patients in the FMT group and 3/7 (43%) controls were decolonized; for samples collected at >6 weeks, 4/4 (100%) in the FMT group and 6/7 (86%) in the control group were decolonized. These results from subgroup analyses were not statistically significant given the high rate of spontaneous VRE decolonization.

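### The primary outcome counts any negative Day 10 culture as decolonization and uses no pre-dose VRE result, so participants who cleared VRE before dosing are successes in both arms

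*Combined protocol and SAP*

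**What the plan says.** The primary efficacy outcome (Protocol Summary and C.3.2.1) is the proportion of participants with VRE decolonization at Day 10 (± 3 days), where "VRE decolonization is defined by absence of VRE on stool culture using standard clinical laboratory techniques". The definition sets no condition on VRE status at dosing.

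Inclusion criterion 3 (C.5.1) requires a positive stool culture in the preceding 14 days. C.4 counts that window back from randomization. C.7.6 counts it from the Enrollment visit and asks for an Enrollment stool only if one is needed, because a "VRE positive screened sample 14 days prior to Enrollment visit is acceptable".

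Other sections point the other way. C.7.2.2 has a stool sample collected before the intervention is given, and the visit table (C.17.2) lists a stool sample and ARB PCR at Visit 2. No section requires a VRE culture on that stool or uses its result in the analysis. C.5.3.4 commits to intention-to-treat. C.10.2 names no primary test, no primary analysis set and no rule for participants who are negative at baseline.

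The preliminary study (C.2.2 and C.16.1) used a conditional definition: "VRE decolonization was defined as absence of VRE colonization post-FMT among a patient colonized with VRE pre-FMT". The sample size (C.10.1) uses a "conservative estimate of 85% decolonization in FMT group, 40% in control group with power=0.9" and describes these rates as "in keeping with preliminary data and a conservative 15% drop-out rate".

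**The concern.** The outcome measures absence of VRE at Day 10. It does not measure loss of VRE that was present at dosing. The two differ for anyone who cleared between the qualifying sample and Day 0: that participant cannot be decolonized by either product, yet counts as a success in whichever arm they join.

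Two things are at stake. The first primary objective is the decolonization rate of FMP-402 versus placebo, and both reported rates would include clearances that happened before treatment. Also, adding the same block of successes to each arm narrows the difference, so the trial could have less power than planned if the planning rates describe current carriers. Without a culture result from Day 0, neither effect could be measured or corrected afterwards.

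**Working it through.** **Inputs from the documents.** Rates 85% and 40%, power 0.9, alpha 0.05, 15% drop-out, N = 46 (C.10.1); two-sided testing (C.10.2); "23 in the treatment group and 23 in the placebo group" (Protocol Summary); mean VRE persistence of 26 weeks (C.2.1); 3/7 controls clear in samples taken at 6 weeks or earlier (C.16.1).

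**Input not in the documents.** f, the share already clear at dosing.

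**1. The plan's figure.** Two proportions, unpooled variance, two-sided 0.05, 90% power:

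n = (1.96 + 1.2816)² × (0.85×0.15 + 0.40×0.60) / 0.45² = 19.07, so 20 per arm. Then 20 × 1.15 = 23 per arm, or 46. The stated size reproduces. (Dividing by 0.85 instead gives 24 per arm, or 48.)

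**2. A range for f.** Assume a constant clearance hazard h per week, so f = 1 − exp(−h × weeks since the qualifying sample).

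- 26-week mean: h = 1/26 = 0.0385.
- 3/7 clear, read as at a full 6 weeks: h = −ln(4/7)/6 = 0.0933.

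| Age of qualifying sample | f from 26-week mean | f from 3/7 by 6 weeks |
|---|---|---|
| 7 days | 3.8% | 8.9% |
| 14 days | 7.4% | 17.0% |

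Averaging the 26-week figure over sample ages spread evenly from 0 to 14 days gives 3.7%. The second hazard rests on 7 patients and would be higher if their samples were taken well before 6 weeks.

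**3. Effect on the reported placebo rate.** On the same hazards, total control clearance from a 14-day-old sample to Day 10 (24 days) is 12.4% or 27.4%. The part before dosing is 7.4 of 12.4 points or 17.0 of 27.4 points, about 60% either way. For a 7-day-old sample it is 3.8 of 8.9 or 8.9 of 20.3 points, about 43%.

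**4. Effect on power, if 85%/40% apply to participants colonized at dosing.** Assume early clearers stay negative. Each rate becomes f + (1 − f)p, so the difference becomes 0.45(1 − f). At f = 10% the rates are 0.865 and 0.460, a difference of 0.405. Exact power comes from enumerating all binomial outcomes. C.10.2 names no test, so two are shown:

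| f | 23 per arm: Pearson / Fisher | 20 per arm: Pearson / Fisher |
|---|---|---|
| 0 | 0.913 / 0.853 | 0.873 / 0.797 |
| 3.7% | 0.894 / 0.828 | – |
| 10% | 0.859 / 0.781 | 0.816 / 0.719 |
| 17% | 0.814 / 0.725 | – |

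The 20-per-arm column reflects the planned drop-out (23 × 0.85 = 19.55).

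**5. If 85%/40% already include pre-dose clearers,** the observed rates are 85% and 40% by assumption and planned power is the same at every f.

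**6. What restricting to pre-dose positives gains** (85% vs 40%, full retention, compared with all randomized at 23 per arm):

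- f = 3.7%, 22 per arm: Pearson 0.895 vs 0.894; Fisher 0.827 vs 0.828.
- f = 10%, 21 per arm: Pearson 0.891 vs 0.859; Fisher 0.799 vs 0.781.

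**The case against.** **The planning rates may already allow for this.** C.16.1 conditions on colonization before FMT but does not say how old the pre-FMT sample was, and the trial's own entry rule also conditions on an earlier positive. The two may be like for like. The control clearance implied by the documents' figures (12% to 27% from a 14-day-old sample) is below the planned 40%, which may therefore cover early clearers. This stands. A reader might infer that the sizing assumes a population of current carriers and that planned power is therefore lost; the documents do not establish that.

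**Larger values of f are not supported.** A reader might treat the planned 40% as natural clearance per 10 days and obtain f = 1 − 0.6^0.7 = 30% for a 7-day-old sample, or 1 − 0.6^1.4 = 51% at 14 days. That hazard implies a mean persistence of about 20 days (10 / −ln 0.6), against 26 weeks in C.2.1. It also implies 88% of controls clear by 6 weeks (1 − 0.6^4.2), against 3/7 in C.16.1. Nor does any section link the 48-hour antibiotic rule to clearance before dosing.

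**There is no bias between arms.** Randomization balances early clearers on average, and chance imbalance is part of ordinary sampling variation. This stands.

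**Intention-to-treat is a legitimate primary choice.** Whether to estimate the effect in all randomized participants or in Day 0 carriers is a question of estimand, and step 6 shows little or modest power gain from restriction. This stands against replacing the primary set. It does not answer the need for a Day 0 result.

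**Baseline status may already be obtained.** ARB PCR is scheduled at Visit 2, and one of the two ARB definitions includes VRE. But PCR is not the culture that defines the primary outcome, C.7.6 makes the Enrollment stool conditional, and no analysis uses the result.

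**Conclusion.** The point holds as one of measurement and estimand. As written, a participant who cleared VRE before dosing is scored as decolonized in either arm, and nothing in the plan identifies such participants. Both reported rates are raised and the difference may be diluted.

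The size depends on f, which the documents do not give. About 4-9% (7-day-old sample) to 7-17% (14-day-old sample) follows from their own figures under a constant hazard. If the planning rates describe participants colonized at dosing and early clearers stay negative, the Pearson power loss at 23 per arm is about 2 points at f = 3.7%, 5 points at 10% and 10 points at 17%. If the rates already include early clearers, there is no loss of planned power, but the reported rates still mix clearance before and after dosing. This merits a change to the protocol. It does not show that the trial is undersized or that its comparison is biased.

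**What to change.** 1. Reconcile C.7.2.2 and C.17.2 (stool collected at Visit 2) with C.7.6 (only if needed), so that every participant has a stool collected before dosing.
2. Run the VRE culture on that stool by the method used at Day 10, without holding dosing for the result.
3. Keep all randomized participants as the primary set, in line with C.5.3.4.
4. Pre-specify in C.10.2, as the key supporting analysis, decolonization defined as pre-dose culture positive and Day 10 culture negative, compared between arms among participants who were pre-dose positive. The sample predates treatment, so this restriction preserves the randomized comparison.
5. State in C.10.1 whether 85% and 40% are conditional on a positive culture at dosing.

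The cost is one routine culture per participant, a stool collection for anyone who would have been enrolled on an earlier sample alone, and a few lines of text. The supporting set will be slightly smaller than the randomized set (about 21 per arm at f = 10%, before drop-out).

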5. Males must agree to avoid impregnation of women during and for four weeks after completing study treatment. through use of an acceptable method of contraception.

Note: §Includes, but is not limited to, barrier with additional spermicidal foam or jelly, intrauterine device, hormonal contraception (started at least 30 days prior to study enrollment), intercourse with men who underwent vasectomy.

C.5.2 Participant Exclusion Criteria

Participants will not be able to participate if they meet any of the following exclusion criteria:

1. Female patient who are pregnant, lactating or planning on becoming pregnant during study. Female patients of childbearing potential will undergo a pregnancy test, and be excluded from the study if positive.
2. Inability (e.g. dysphagia) to or unwilling to swallow capsules.

3. Active antibiotic-resistant bacteria (ARB) or gastrointestinal infection at time of enrollment.
4. Patient received antibiotics in the last 48 hours. Patients will be eligible to enroll if antibiotic therapy is discontinued for at minimum 48 hours prior to randomization. Does not include antibiotics used for prophylaxis or topical antibiotics.
5. Requires continued antibiotic use or anticipates antibiotic use in the upcoming 4 weeks. Does not include antibiotics used for prophylaxis or topical antibiotics.
6. Unwilling to withhold probiotics for a minimum of 48 hours prior to providing a screening stool sample.
7. Known or suspected toxic megacolon and/or known small bowel ileus.
8. Major gastrointestinal surgery (e.g. significant bowel resection) within 3 months before enrollment. This does not include appendectomy or cholecystectomy.
9. History of total colectomy or bariatric surgery.
10. Admitted to or expected to an intensive care unit for medical reasons (not just boarding). Patients residing in a nursing home, long-term care facility or rehabilitation center may be enrolled.
11. Concurrent intensive induction chemotherapy, radiation therapy or biological treatment for active malignancy. Patients on maintenance chemotherapy may be enrolled only after consultation with medical monitor.
12. Unable or unwilling to comply with protocol requirements.
13. Expected life expectancy < 6 months
14. Previous FMT or microbiome-based products at any time excluding this study.
15. Patients with a history of severe anaphylactic or anaphylactoid food allergy.
16. Solid organ transplant recipients ≤ 90 days post-transplant or on active treatment for rejection.
17. Neutropenia (≤ 500 neutrophils/mL) or other severe immunosuppression. Anti-TNF will be permitted. Patients on monoclonal antibodies to B and T cells, glucocorticoids, antimetabolites (azathioprine, 6-mercaptopurine, methotrexate), calcineurin inhibitors (tacrolimus, cyclosporine) and mycophenolate mofetil may be enrolled only after consultation with the medical monitor.
18. If at risk for CMV/EBV associated disease (e.g immunocompromised), negative IgG testing for cytomegalovirus (CMV) or Epstein Barr Virus (EBV).
19. A condition that would jeopardize the safety or rights of the subject, would make it unlikely for the participant to complete the study, or would confound the results of the study.

C.5.3 Treatment Assignment Procedures

C.5.3.1 Randomization Procedures

Participants who fulfill the criteria for randomization, will be randomized on a 1:1 basis with a with random permuted blocks (size of 2 or 4) to receive FMP-402 or placebo. Participant's randomization will be carried out by a bioinformatician based at OpenBiome using random number generation software to create a randomization schedule.

C.5.3.2 Masking Procedures

This is a double blinded placebo controlled trial where both the participant and treating physicians will be blinded. FMP-402 or placebo will be dispensed by OpenBiome thereby maintaining blinding of study clinician. Packaging will be identical and consist of the same saline and glycerol buffer used in FMT processing without the addition of microbiota.

Under normal circumstances, the blind should not be broken. The blind should be broken only if specific emergency treatment would be dictated by providing the treatment the participant was receiving. In such cases, the site PI must contact the Medical Monitor to request that the blind be broken. For participants who require unblinding, this information will be captured in the case report form (CRF).

The randomization schedule will be maintained by OpenBiome. Study participants or legal guardians will remain blinded and not be provided any information until all participants have completed the trial.

C.5.3.3 Reasons for Withdrawal

A participant may withdraw from the study at any time for any reason, without any consequence. A participant may be withdrawn from the study by the site PI for the following reasons:

Adverse event that may make it no longer in the best interest of the subject to continue participation in the study

Participant choice (withdrawal of consent)

Protocol violation/non-compliance

Pregnancy

Lost to follow up

Other (must be noted)

C.5.3.4 Handling Withdrawals

The primary reason for withdrawal from the study will be recorded on the Study Status CRF page. Participants will be encouraged to complete the Early Termination Visit. The Early Termination Visit procedures are listed. Although participants are free to withdraw at any time, participants will be encouraged to remain in the study for follow-up safety evaluation. Every attempt should be made to follow all AEs and SAEs ongoing at the time of early withdrawal to resolution or until stabilized. If possible, a final stool sample will be collected at the Early Termination Visit. Intention-to-treat analysis will be utilized according to best practices in clinical trials. Attempts will be made to complete safety follow-up for all subjects who have received the study product, including those who have discontinued participation in other study procedures, for the duration of the planned follow-up period.

Participants who are withdrawn from the study after randomization but before intervention or placebo will be replaced. Possible reasons for participant withdrawal after randomization include but are not limited to:

- Participants who are started on a new course of antibiotics after randomization and before intervention/placebo
- Unrelated participant death

C.5.3.5 Termination of Study

In the unlikely event that significant safety concerns arise, the PIs can terminate or halt the study pending review by the DSMB. In addition, this study may be halted early based on the DSMB charter or FDA recommendations.

C.6. STUDY INTERVENTION/INVESTIGATIONAL PRODUCT

C.6.1 Study Product Description

FMP-402 is encapsulated fecal microbiota sourced from human-derived microbes. The human source generating the fecal microbes has been extensively screened for infectious pathogens and microbiome mediated diseases using a standardized process (found in OpenBiome's BBMF # 15543, Section F). Additionally, the capsule delivery vehicle enables targeted deposition of the investigational active pharmaceutical ingredient into the colon.

C.6.2 Formulation

C.6.2.1 Encapsulated fecal microbiota preparation (formulation FMP-402)

This formulation is encapsulated fecal microbiota sourced from human-derived microbes generated by healthy, screened donors, as described in OpenBiome's [REDACTED]

BBMF # 17300

C.6.2.2 Placebo

Placebo capsules will be identical in appearance to FMP-402 capsules but will not have human feces, [REDACTED]

[REDACTED] processed as described in OpenBiome's BBMF #

17300 [REDACTED]

C.6.3. Product Storage and Stability

Produced material will be stored at -80°C and each unit will have a date of production printed on it for tracking purposes. Studies have been conducted to ensure long-term bacterial viability following the freezing process based on studies conducted by Hamilton et. al and Youngster et. al.^{40,41} Local site storage at -20°C will be permitted for up to 6 months.

FMP-402 is currently undergoing stability testing, therefore expiration dates will not be provided with each unit. Instead, storage requirements will be provided via correspondence from the manufacturing company, Finch Therapeutics. Results from ongoing stability testing will be provided by Finch Therapeutics to partner sites, through OpenBiome, on an anticipated monthly basis. If units are determined to be unstable, Finch Therapeutics will communicate with OpenBiome to destroy the relevant units.

C.6.4 Dosage, Preparation and Administration of Study Intervention/Investigational Product

Participants will receive a single dose of 30 FMP-402 or placebo capsules. The dosing rationale is driven by the successful VRE decolonization for 2 patients with recurrent CDI and co-colonization of VRE following a single dose of 30 OpenBiome FMT capsules. Participants will undergo capsule administration by the following process:

- Document Review: Confirmation/review of exclusion criteria/contraindications as previously described.
- Safety Capsules: Direct observed capsule test, where participants will ingest one inert, size 00 ‘safety’ capsule under direct supervision of the study physician/nurse.
- Dietary instructions: Patients should maintain a clear liquid diet the day of administration and should fast (NPO) for a minimum of 2 hours prior to administration
- Capsule administration:
 - a. Patient should ingest 30 capsules (FMP-402 or placebo) under the direct observation of a physician/nurse. Patients may have water during capsule administration.
 - b. Patient should ingest capsules after extraction from freezer, and no longer than 60 minutes after removal.
 - c. Patients should remain fasting (NPO) for 1 hour following ingestion but may then return to a full diet.

C.6.5 Accountability Procedures for the Study Intervention/Investigational Product

The site principal investigator (PI) (or designee) will maintain an accurate record of the receipt of the investigational materials as shipped, including the date received. One copy of this receipt will be returned to OpenBiome when the contents of the investigational materials shipment have been verified. In addition, the unblinded laboratory technician based at OpenBiome will maintain a log of all clinical trial materials (FMP-402 and placebo) dispensed. This clinical trial material accountability record will be available for inspection at any time.

C.6.6 Modification of Study Intervention/Investigational Product for a Participant

If the participant is unable to complete the full dose of FMP-402 or placebo, the following modification will take place. The dose will be recorded and the remainder of capsules will be offered to participant the same day at the discretion of the treating physician. Intention-to-treat analysis will be utilized according to best practices in clinical trials.

C.6.7 Assessment of Participant Compliance with Study Intervention/Investigational Product

FMP-402 or placebo capsules will be consumed under direct supervision of study staff.

C.6.8 Concomitant Medications/Treatments

Given the participants with VRE colonization and who are most at risk for VRE infection are patients with multiple comorbidities, all medications will be accepted in this study, at the discretion of the treating physician. This includes, but is not limited to:

1. Anti-hypertensive therapies
2. Heart failure medications
3. Diuretics
4. Laxatives
5. Topical medications
6. Anti-depressants
7. Statins
8. Diabetic medication
